#### 2 STUDY OBJECTIVES

- **2.1** Primary Objectives
- 2.1.1 Develop IntelliCare and optimize its functionality through laboratory and field usability testing.
- 2.1.2 Develop the machine learning models and algorithms that will continuously learn from user interactions with IntelliCare to provide intervention recommendations and motivational messaging.
- 2.1.3 Conduct a randomized controlled trial (RCT) comparing 8 weeks of IntelliCare with the machine learning component to 8 weeks of IntelliCare without the machine learning component for the treatment of depression and anxiety. Participants will be evaluated at baseline, week 4, week 8, and at 3- and 6-month post-treatment follow-ups. It is hypothesized that 1) IntelliCare with the recommendations, in contrast to IntelliCare without the recommendations, will produce greater adherence and greater reductions in depressive and anxiety symptoms and 2) IntelliCare with coaching will produce greater greater adherence and greater reductions in depressive and anxiety symptoms. The primary patient centered outcome will be depression/anxiety severity.
- 2.2 Secondary Objectives.
- 2.2.1 Exploration of the mediating effects of adherence markers (e.g. time in treatment, app launches, etc.) coaching variables (e.g. message frequency, timing, etc.), and psychological variables (e.g. change in self-report measures) on depression and anxiety outcomes.
- **2.2.2** Exploration of moderating variables on outcomes, such as baseline demographics, baseline characteristics.
- 2.2.3 Explore, optimize, and validate coaching methods.

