# PHASE 3 RANDOMIZED CONTROLLED TRIAL

- 4.1.4 Phase III Randomized Controlled Trial. For the RCT, 300 participants meeting entry criteria will be enrolled over 13 months (approximately 23 per month). Participants will be randomized using a factorial design with the following factors:
- **4.1.4.1** Factor 1. Hub App with intelligent recommender system/Hub app without intelligent recommender system: This factor is consistent with Objective 2.1.3 on pg. 4
- **4.1.4.2** Factor 2. Coaching/No Coaching: This factor would allow us to examine and control for the effect of coaching.
- **4.1.5** *Phase III Enrollment.* Participants in the RCT will be enrolled remotely to avoid excluding individuals with access barriers who are among those who would be likely end users. Screening will be conducted in 3 stages.
- 4.1.5.1 Screening Stage 1 (pre-consent): Interested parties will complete a brief web screen to determine whether there is any reasonable expectation that they might be eligible (data from the brief screen will be included in the study dataset). If they are clearly not eligible they will be informed of this and thanked. If they appear to be eligible a research assistant will follow-up by phone to clarify responses from the web screen and ask additional phone screening questions. If the participant passes the stage 1 phone screen s/he will be invited to initiate the online consent process and proceed to screening stage 2 described below.

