- 6.9.2 Preliminary data indicates that approximately 50% of patients stop participating in BITs (which we define here as "drop out") by week 7 (see Sec. D.1.1). A sample size of 135/arm (total sample of 270) will provide 80% power to detect a difference in median drop out time from 7 to 10 weeks. We estimate from existing data (Sec D.1.1) that a 3 week increase would result in an 11% improvement in depression severity (ES=0.30). Additionally, this sample provides 80% power to detect an increase in continued participation from 50% to 61.6% at week 7. Both analyses are based on a log-rank test at a type 1 error rate of 5%, with accrual of 54 weeks and 12 weeks of intervention. Power for continuous patient

centered outcomes were based on independent t-tests, and would have 80% power to detect effect sizes of 0.34. Power calculations were performed using Pass 2008.(Hintze, 2008)

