#### **6.10** Adherence Outcomes:

- 6.10.1 The primary outcome will be time to last use of a treatment element (lesson or tool), and will be tested between groups using traditional survival (Kaplan-Meier) methods, where the event of interest is last use from intervention start. Secondary analyses of the primary outcome would include Cox regression models that would adjust for potential effect modifiers or moderators such as gender, race, and age.
- **6.11** Patient Centered Outcomes:
- 6.11.1 Although power was presented for independent t-tests, primary analyses for patient centered outcomes (QIDS-C, MDD, and PHQ-9) will utilize generalized linear mixed (GLM) models (with link functions depending on the distribution of the outcome), that can examine patterns over the course of treatment and follow-up, and can account for missing data.(Gibbons et al., 1993)
- **6.12** Secondary Mediation Analyses:
- 6.12.1 Mediators will be entered into our models as time-varying covariates. We used the framework of Muller and colleagues(Muller, Judd, & Yzerbyt, 2005) to identify those variables, which mediate the effects of treatment on depression. Only if the 4 criteria specified by Muller are satisfied (treatment effect for depression, treatment effect for the mediator, effect of mediator on depression, and reduction of treatment effect when mediator is included), will we calculate the effect of mediation using MacKinnon and colleagues' product of coefficients method.(MacKinnon, Lockwood, Hoffman, West, & Sheets, 2002) Bias-corrected 95% confidence intervals for the mediated effect will be calculated using bootstrapping.(Shrout & Bolger, 2002)
- 6.12.2 Development of the recommendation engine algorithms will use machine learning and Baysean. statistical methods that will continuously learn that will continuously learn from user interactions with IntelliCare to provide intervention recommendations.
- **6.12.3** Exploration of moderating variables on outcomes, such as baseline demographics, baseline characteristics.
- 2.2.3 Explore, optimize, and validate coaching methods. This will include analyses of all data captured in the delivery of coaching, including the timing and content of messages and phone calls, and coach records related to participant encounters.

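### Section 6.12.1 calculates the mediated effect only after four criteria are met. At the expected effect of 0.30 this loses about a fifth to a third of the power to detect mediation.

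*Combined protocol and SAP*

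**What the plan says.** Objective 2.2.1 is secondary and reads "Exploration of the mediating effects of adherence markers", together with coaching and psychological variables, on depression and anxiety outcomes. It gives examples of mediators but no closed list.

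Section 6.12.1 sets the method for the randomised trial. Mediators enter the models as time-varying covariates. Four criteria must be satisfied: "treatment effect for depression, treatment effect for the mediator, effect of mediator on depression, and reduction of treatment effect when mediator is included". Only then, it says, "will we calculate the effect of mediation using" the product-of-coefficients method. It adds: "Bias-corrected 95% confidence intervals for the mediated effect will be calculated using bootstrapping". No test or significance level is given for any criterion, and nothing says what is reported if one fails. The criteria name depression only.

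Section 6.8.1 repeats the rule for the Phase II field trial, which section 4.1.3 describes as an 8-week study with a single arm.

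Section 6.9.2 bases power on 135 per arm (270 in total). It expects a three-week gain in median use to yield an effect of 0.30 on depression, and says continuous outcomes "would have 80% power to detect effect sizes of 0.34". Section 4.1.4 states that "300 participants meeting entry criteria will be enrolled over 13 months", in four groups of 75.

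**The concern.** The product of coefficients with a bootstrap interval already answers the statistical question of whether the indirect effect differs from zero. The four criteria add nothing to that estimate; they decide whether it is calculated at all. The weak link is the total treatment effect on depression, because the trial expects 0.30 but is sized for 0.34.

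Section 6.9.2 derives the expected depression effect from the expected adherence gain, so the path from adherence to symptoms is the trial's own rationale. If the total effect narrowly misses significance, the plan gives no indirect estimate and no interval, at the point where information on mechanism would help explain the result. When estimates are reported, they have been selected for being large.

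In the field trial, two of the four criteria refer to a treatment effect that a single arm cannot supply as a between-group contrast.

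**Working it through.** **1. The plan's own figure.** For a two-group comparison with n per group and standardised effect d, two-sided 5%, power is approximately Φ(d√(n/2) − 1.96). The plan does not state sidedness; two-sided reproduces its figure.
- n = 135, d = 0.34: 0.34 × 8.216 = 2.793; Φ(0.833) = 79.8%. The plan says 80%, so it reproduces.

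**2. Power of the depression criterion alone**, read as that same test. The 150 per factor level follows from four groups of 75.

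| Total effect | n = 135 | n = 150 |
|---|---|---|
| 0.34 | 79.8% | 83.8% |
| 0.30 | 69.3% | 73.8% |
| 0.20 | 37.6% | 41.0% |
| 0.15 | 23.3% | 25.4% |

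For example, n = 135 and d = 0.30 gives 0.30 × 8.216 = 2.465 and Φ(0.505) = 69.3%. All four criteria must hold, so this column is a ceiling on how often the estimate can be calculated, however strong the mediation is.

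**3. The fourth criterion.** In linear models the drop from the total to the direct effect equals a × b, where a is treatment to mediator and b is mediator to outcome. Read as a smaller coefficient, this criterion adds almost nothing to the tests of a and b.

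**4. Gated against ungated.** The documents give no values for a or b, so these are assumptions: a = 0.34 or 0.50 SD, b = 0.3 to 0.6. The simulation used least squares, 8,000 trials per setting and two-sided 5% on each path. Ungated means a and b are both significant; gated means all four criteria hold. Share lost = 1 − gated/ungated. Simulation error is about one percentage point.

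| n per level | a | b | Total effect | Ungated | Gated | Share lost |
|---|---|---|---|---|---|---|
| 135 | 0.34 | 0.4 | 0.30 | 80% | 60% | 25% |
| 135 | 0.34 | 0.6 | 0.30 | 80% | 62% | 22% |
| 135 | 0.50 | 0.6 | 0.30 | 98% | 69% | 30% |
| 150 | 0.34 | 0.6 | 0.30 | 83% | 67% | 20% |
| 150 | 0.50 | 0.6 | 0.30 | 99% | 73% | 26% |
| 135 | 0.34 | 0.4 | 0.34 | 80% | 67% | 16% |
| 135 | 0.34 | 0.6 | 0.204 | 79% | 36% | 54% |
| 135 | 0.50 | 0.4 | 0.20 | 98% | 37% | 62% |

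The rows with a = 0.50 and b = 0.6 give a × b = 0.30. They are the closest to the plan's argument that the whole 0.30 comes through adherence.

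Over all settings the share lost is 11-20% at a total effect of 0.34, 20-31% at 0.30, 51-63% at about 0.20, and 74-85% at 0.10-0.15. At 0.30 the power ranges are about 59-73% gated and 79-99% ungated.

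**5. Check with the planned interval.** A bias-corrected bootstrap (500 trials, 400 resamples) at 135 per arm, a = 0.34, b = 0.4 and total 0.30 excluded zero in 85% of trials. The gate passed 63%. This agrees with the table.

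**6. Size of the reported estimates.** The ungated mean is 0.99-1.05 times the true value. The gated mean is 1.03-1.24 times. Selecting on a and b alone already gives 1.00-1.14, so the depression criterion adds roughly 0.01-0.12.

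**The case against.** **A pre-specified, conservative gate suits an exploratory objective.** Mediators are open-ended, there are two factors, and no multiplicity control is stated. The exploratory status stands and limits how much weight this point carries. The false-positive argument is weaker. When no mediation exists, the ungated joint test of the two paths stays at about 5% per mediator. That check concerned the joint test rather than the bias-corrected interval, and it does not address multiplicity across mediators.

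**The model checked is not the planned one.** The planned analysis is a mixed model with time-varying mediators on 300 participants, and the criteria carry no stated test. This stands. The 69% comes from a t-test on 270; with 300 it is about 74% before attrition. The percentages should be read as indicative.

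**Stronger readings that the documents do not support:**
- A reader might infer that the gate discards most of the power. At 0.30-0.34 it does not: the loss is 11-31%. A smaller total effect is plausible, because every group receives the treatment apps, entry on anxiety alone is allowed, and section 6.9.2 assumes 12 weeks of intervention while the trial gives 8. How much smaller is an assumption.
- A reader might infer that the adherence result goes unreported. Section 6.10.1 tests adherence as the primary outcome regardless. Only the product estimate and its interval are withheld.
- A reader might blame all the inflation on the depression criterion. Much of it comes from testing the mediator paths when a is weak.
- A reader might take the bootstrap interval as proof of mediation. Adherence is not randomised, so confounding and reverse causation remain open.

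**Conclusion.** The point holds as a modest loss with an inexpensive remedy. Section 6.12.1 makes the estimate that objective 2.2.1 calls for depend on a significant depression effect. At the plan's expected effect of 0.30 this costs about a fifth to a third of the power to detect mediation, and it costs more than half only if the true total effect is about 0.20 or less. The upward bias in what is reported is about 3-24%, shared between the mediator-path and depression criteria.

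The sizes rest on the assumed paths, a single continuous mediator, linear models, each criterion read as a two-sided 5% test, one factor at a time, and no missing data. The direction does not depend on the assumed paths: adding a required test can only reduce how often the estimate is calculated.

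The field-trial defect is separate. Section 6.7.1 plans dependent t-tests, so someone might read the pre-post change as the treatment effect, but section 6.8.1 does not say so. Deleting the gate there would not create the treatment-to-mediator contrast that the product of coefficients needs.

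**What to change.** In section 6.12.1:
- Delete the condition that makes the calculation depend on the four criteria.
- Name the mediators, at least the primary adherence measure (time to last use).
- Calculate and report the product-of-coefficients effect with its bootstrap 95% interval for each named mediator and each factor, for PHQ-9 and GAD-7, whether or not the total effect is significant.
- Report the four criteria descriptively and label the results exploratory.

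In section 6.8.1, replace the mediation rule with a description of the association between app use and symptom change.

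The cost is SAP wording and more estimates to present; no design change or new data are needed. The extra estimates carry no multiplicity control, and each indirect effect still rests on the assumption of no confounding between mediator and outcome. The report should say both.

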# 7 STUDY MANAGEMENT

- 7.1 Conflict of Interest.
- 7.1.1 Any investigator who has a conflict of interest with this study (patent ownership, royalties, or financial gain greater than the minimum allowable by their institution, etc.) must have the conflict reviewed by

- Northwestern University Conflict of Interest Office. All investigators will follow the University conflict of interest policy.
- 7.2 Institutional Review Board (IRB) Approval and Consent
- 7.2.1 It is expected that the IRB will have the proper representation and function in accordance with federally mandated regulations. The IRB should approve the consent form and protocol.
- 7.2.1.1 In obtaining and documenting informed consent, the investigator should comply with the applicable regulatory requirement(s), and should adhere to Good Clinical Practice (GCP) and to ethical principles that have their origin in the Declaration of Helsinki.
- 7.2.1.2 Before recruitment and enrollment onto this study, the patient will be given a full explanation of the study and will be given the opportunity to review the consent form. Each consent form must include all the relevant elements currently required by the FDA Regulations and local or state regulations. Once this essential information has been provided to the patient and the investigator is assured that the patient understands the implications of participating in the study, the patient will be asked to give consent to participate in the study by signing an electronic IRB-approved consent form. On this consent form, participants will have additional opportunities to provide separate consent for: 1.) contact regarding future research opportunities and 2.) permission to use anonymous quotes from opinions they have expressed about the IntelliCare apps during the course of the study for use in the design of future digital interventions, promotional recruitment materials, Center for Behavioral Intervention Technologies website, research papers, presentations, and media stories.

